10.2. Primary Variables

The primary variables for the analysis of heart rate (HR) and respiratory rate (RR) are each the overall mean root mean square difference (RMSD), defined as the mean of the individual subject RMSDs. For each subject, the RMSD is calculated as:

$$\text{RMSD} = \text{sqrt}\{ \sum (Y_R - Y_G)^2 / n \}$$

where Y_R and Y_G are the paired values for the RHEA Vital Sign Vigilance System and the gold standard method (Patient Monitor), respectively, and n is the number of data pairs. If motion or a bed exit occurs within 20 seconds preceding the recording period for a given data pair, the data pair at that time point will not be used in the analysis. A total of 20 pairs of measurements are

planned for each subject. If more than 20 measurements are collected for a subject, then only the first 20 will be used. If fewer than 20 measurements are collected for a subject for any reason, that subject will still be included in the analyses.

The primary hypotheses for HR, are as follows:

Adults

$H_0: \mu = 3.25$

vs.

$H_A: \mu < 3.25$,

The primary hypotheses for RR, are as follows:

Adults

$H_0: \mu = 2.25$

vs.

$H_A: \mu < 2.25$,

where μ represents the population mean HR or RR.

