2.2. Study Objectives

This clinical trial aims to verify that the RHEA Vital Sign Vigilance System can fulfill its intended use and meet its declared performance and functional specifications. Statistical analysis comparing the performance of the RHEA Vital Sign Vigilance System and the reference device EarlySense System 2.0 to the MP/MX series separately aims to demonstrate that the investigational device is substantially equivalent to the cleared reference device-EarlySense System 2.0 in safety and effectiveness.

3. Study Design

This will be a cross-over, ‘self-controlled’ study comparing the investigational device RHEA Vital Sign Vigilance System to an approved under-mattress device, EarlySense System (Model 2.0) (K131379). Both will be compared to the ‘gold standard’ Philips MP/MX series model Patient Monitor. The same Monitor Device must be used across all hospital wards in this study.

The testing will be conducted in three periods. In the Accuracy Tests (periods 1 and 2), one of the contact-free devices will be used to monitor the HR and RR, while being compared with the MP/MX series Patient Monitor. The RHEA investigational device and reference device will be used to monitor the same subject at different times (cross-over design), as the sensors of the two devices are placed at a similar location of the bed. HR and RR will be recorded for all three devices. Comparison of the performance of the two contact-free devices will be performed on the recorded results via statistical analysis. The third test will assess the ability of the RHEA device to accurately detect motion on or exit from the bed, as compared to the manual observation.

Three clinical trial sites will be selected in the U.S. A total of 77 adult subjects will be enrolled to complete 73 subjects (5% drop-out rate anticipated). Please see Section 10 for Sample Size justification. A site may enroll no more than half the total number of subjects for the study; i.e., up to 39 total subjects per site. It is anticipated that 33 days are needed for 77 recruited patients in total.

The testing duration for each subject will be one to two hours, including device placement, measurements, and device removal.

This is a multi-center study to be conducted in three hospitals. Wards in each site should be representative of non-ICU wards in U.S. hospitals (e.g., medical/surgical, oncology, orthopedics, long term acute care).

4. Subject Selection

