6.3. Testing Procedures

The test will be conducted in three parts:

- Reference Device accuracy test
- Investigational Device accuracy test
- Motion and bed exit test

The following terms are used in the testing procedures below:

- Investigational Device (RHEA device)
- Reference Device (EarlySense device)
- Monitor Device (Gold Standard MP/MX series device)

Reference Device Accuracy Test

1. Two testers (Reference Device tester and Monitor Device tester) will record the following subject information in the CRF: subject ID, gender, height, weight, primary clinical diagnosis, time, site location (hospital and ward).
2. Place the Reference Device sensor unit under the mattress and beneath the chest of the subject according to the instructions for use. Place the bedside unit on a flat surface.
3. Synchronize the date and time of the Reference Device and the Monitor Device (to be equivalent).
4. Place the main units of the Reference Device and the Monitor Device in different locations in the subject's room such that they can only be viewed by their respective testers.
5. After the subject lies down on the bed, place the Monitor Device lead on the subject's chest

in accordance with the operational instruction of the Monitor Device.

6. Connect the etCO₂ module to the Monitor Device and apply the nasal cannula to the subject.
7. Turn on the Monitor Device and the Reference Device. Set the Monitor Device to “real-time monitoring mode”.
8. Instruct the subject to remain motionless. At one-minute intervals, the two testers will simultaneously record the heart rate (HR), respiratory rate (RR) and the current time using their respective device.
9. If the HR or RR value does not appear, or turns blurred on the screen (in this state only the last value is displayed rather than the current value), the Reference Device tester will mark it on the CRF.
10. Stop the test once 20 valid pairs of data are recorded for each subject. If certain values are marked (per Step 9 above), the data at that recorded point will not be considered in the analysis. More than 20 pairs will be collected in order to ensure that there are at least 20 valid pairs.

Investigational Device Accuracy Test:

1. Two testers (Investigational Device tester and the Monitor Device tester) will record the following subject information in the CRF: subject ID No., gender, height, weight, primary clinical diagnosis, time, site location (hospital and ward).

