2. Place the Investigational Device sensor unit under the mattress and beneath the chest of the subject. Place the bedside unit on a flat surface or hang on the wall using the bracket.
3. Calibrate the device in accordance with the operator’s manual.
4. Synchronize the date and time of the Investigational Device and Monitor Device (to be equivalent).
5. Place the main units of the Investigational Device and the Monitor in different locations in the subject’s room such that they can only be viewed by their respective testers.
6. After the subject lies down on the bed, place the Monitor Device lead on the subject’s chest in accordance with the operational instruction of the MP/MX series Patient Monitor.
7. Connect the etCO₂ module to the Monitor device and apply the nasal cannula to the subject.
8. Turn on the Monitor Device and the Investigational Device. Set the Monitor Device to “real-time monitoring mode”.
9. Instruct the subject to remain motionless. At one-minute intervals, the two testers will simultaneously record the HR, RR and the current time using their respective device.
10. If HR or RR value does not appear or turns darker and with a mark “?” after the value on the screen (in this state only the last value is displayed rather than the current value), the Investigational Device tester will mark it on the CRF.

11. Stop the test once 20 valid pairs of data are recorded for each subject. If certain values are marked (per Step 10 above), the data at that recorded point will not be considered in the analysis. More than 20 pairs will be collected in order to ensure that there are at least 20 valid pairs.

Motion and Bed Exit Test:

This test will be conducted only on subjects who can move and exit the bed easily.

The Monitor Device tester will ask the subject to turn or move ten times and exit the bed for three times randomly in five minutes. The Monitor Device tester will record the time of these events on the CRF. At the same time, the Investigational Device tester will observe if there is an “unexpected motion” or “bed exit” notification on the screen of the Investigational Device and will record the time of this event on the CRF.

Device Testing Considerations:

1. At the baseline for each subject, make sure the following information is recorded: subject ID, date of birth, gender, height, weight, location, time and clinical diagnosis. Adverse events should be recorded and kept during the tests. The record should be signed by the testers.

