2. It is important that nothing be allowed to shake the bed during the test. Anything that will produce vibration (such as a phone or another person) is not allowed to be on the bed during the test.
3. Make sure there is sufficient stable time before the HR and RR results are recorded for the Investigational Device and Reference Device. Thirty seconds is considered to be reasonable for Investigational Device and 1 min for Reference Device. That is to say, if the subject has to turn, stand up or move during the test, record data 30 seconds after the subject lies down and keeps still again. One minute should be left between two record groups for the independence of the data. If the subject moves or is out of the bed, record data 30 seconds after the subject lies down and keeps still again.

7. Device Safety and Stability Evaluation

Safety and stability data should be recorded in the CRF for Investigational device only.

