10.4. Secondary Analyses

Accuracy of the RHEA will be compared with that of the Reference Device-EarlySense device. The RMSD for the Reference Device will be calculated for each subject in the same manner as described for the RHEA. Mean accuracy will then be compared between the RHEA and the Reference Device by comparing the individual subject RMSDs by a paired t test at the 5% level of significance.

Bland Altman plots will be presented separately for each subject's raw data, including the limits of agreement, for both the RHEA and the Reference Device methods. In addition, Bland Altman plots will be presented for the set of RMSD estimates across all subjects, along with two-sided

95% confidence intervals for their limits of agreement. Finally, Bland Altman plots of the raw data across all subjects will be presented, along with two-sided 95% confidence intervals for their limits of agreement. Methods discussed in Bland, JM and Altman, DG (4) and (5) will be used to calculate the confidence intervals of the limits of agreement due to the lack of independence of the repeated measurements on the same subject.

Motion and no motion accuracy will each be calculated along with their respective two-sided 95% confidence intervals. Motion accuracy will be calculated as the proportion of times that the device correctly detected motion among all actual occurrences of motion detected manually. Non-motion accuracy will be calculated as the proportion of times that the device correctly did not detect motion among all actual occurrences of no motion detected manually.

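### Settling time after movement is 20 s, 30 s or 1 min depending on the sentence, which may keep early Reference Device readings and favour RHEA in the secondary comparison

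*Combined protocol and SAP*

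**What the plan says.** Three places in the combined protocol and SAP set a waiting time after movement.

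- **Section 6.3, Device Testing Considerations**, gives stable times by device: "Thirty seconds is considered to be reasonable for Investigational Device and 1 min for Reference Device". The next sentence restates this as a single instruction: "That is to say, if the subject has to turn, stand up or move during the test, record data 30 seconds" after the subject is lying still again. It names no device. The same 30 s is repeated at the end of the item, again with no device named.
- **Section 10.2** sets the analysis exclusion. A pair is not used in this case: "If motion or a bed exit occurs within 20 seconds preceding the recording period for a given data pair". The start of the recording period is not defined.
- **Section 10.4** says the Reference Device RMSD "will be calculated for each subject in the same manner as described for the RHEA", so the 20 s exclusion applies to that device too.

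On what is recorded, the Reference Device accuracy test says: "At one-minute intervals, the two testers will simultaneously record the heart rate (HR), respiratory rate (RR) and the current time". Testers also mark values that are absent or blurred; of the blurred state the plan says "in this state only the last value is displayed rather than the current value". The RHEA steps are parallel, with a question mark as the display flag. Neither set of steps asks for the time of a movement. The Motion and Bed Exit Test does: "The Monitor Device tester will record the time of these events on the CRF".

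**The concern.** The plan holds that the Reference Device needs twice as long as RHEA to settle, but its working instruction and its analysis filter do not carry that difference through. If testers follow the literal 30 s, RHEA gets its full stable time and the Reference Device gets half. A value that is displayed normally but still settling would be kept and would tend to raise the reference RMSD.

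That RMSD is one side of the paired t test in section 10.4. Section 2.2 states that the comparison of the two devices, each against the monitor, is meant to show that "the investigational device is substantially equivalent to the cleared reference device-EarlySense System 2.0 in safety and effectiveness". An inflated reference RMSD could make RHEA look better than it is, or hide a real RHEA deficit. The same pairs also feed the Reference Device Bland-Altman plots.

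A second problem is that an exclusion based on the time since movement needs that time to be known. The accuracy-test steps do not list it, so the exclusion may be hard to apply, or to check, afterwards.

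**Working it through.** **1. The time rules side by side.** The inputs are the stable times in 6.3 (30 s and 60 s), the unnamed recording instruction in 6.3 (30 s) and the exclusion in 10.2 (20 s). Shortfall = stable time minus rule time. For the 20 s rule this assumes that the recording period starts at the moment of the reading.

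| Rule | RHEA (30 s) | Reference Device (60 s) |
|---|---|---|
| 20 s exclusion (10.2, 10.4) | 30 − 20 = 10 s | 60 − 20 = 40 s |
| 30 s instruction (6.3) | 30 − 30 = 0 s | 60 − 30 = 30 s |

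A Reference Device reading between 30 and 60 s meets the instruction and passes the filter. A RHEA reading at 30 s or later is already settled by the plan's own figure. Readings at 20 to 30 s would arise only if the instruction were breached, and would then be kept for both devices.

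**2. The plan's planning figures.** Section 10.6 uses an RMSD standard deviation of 0.75 and means of 3.0 (HR) and 2.0 (RR), against null values of 3.25 and 2.25. A one-sample t test with a difference of 0.25 and two-sided alpha of 0.05 gives n = 73 with power 0.802, and 73 / 0.95 = 76.8, so 77. The plan's 73 and 77 are reproduced and do not depend on this point. They supply the yardstick in step 5.

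**3. Effect of one early reading on a subject's RMSD (illustration).** Assume that 19 of 20 readings have root mean square error b, equal to the planning mean, and one has error e:

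RMSD = sqrt((19·b² + e²) / 20)

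- RR, b = 2.0, e = 5: sqrt((76 + 25) / 20) = sqrt(5.05) = 2.247, a rise of 0.247. With e = 6: sqrt(5.60) = 2.366, a rise of 0.366.
- HR, b = 3.0, e = 5: sqrt((171 + 25) / 20) = sqrt(9.80) = 3.130, a rise of 0.130. With e = 6: sqrt(10.35) = 3.217, a rise of 0.217.

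**4. Effect on the mean.** Shift = share of subjects with one such reading × rise, with e = 5:

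| Share (assumed) | RR | HR |
|---|---|---|
| 0% | 0 | 0 |
| 10% | 0.025 | 0.013 |
| 25% | 0.062 | 0.033 |
| 100% | 0.247 | 0.130 |

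**5. Yardstick.** Half-width of the 95% confidence interval for the paired difference, assuming an SD of 0.75 for both devices and between-device correlation ρ:

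t(0.975, 72) × 0.75 × sqrt(2(1 − ρ)) / sqrt(73), with t = 1.993

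- ρ = 0: 0.247
- ρ = 0.5: 0.175
- ρ = 0.8: 0.111

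A shift from 10% or 25% of subjects lies below all three half-widths. The RR shift matches the widest of them, 0.247, only if every subject has such a reading. The HR shift of 0.130 in that extreme case exceeds only the half-width at ρ = 0.8.

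**The case against.** The strongest reply is that the 20 s and 30 s figures do different jobs. One says when to record and the other filters afterwards. If testers never record before 30 s, the 20 s filter lets in nothing new. This stands: the sharpest conflict is inside section 6.3, between 1 min for the Reference Device and an unnamed 30 s. The 20 s rule is a backstop too short to repair it, rather than a direct contradiction.

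It can also be said that 6.3 already gives a device-specific time, so a tester who applies 1 min creates no bias. That is correct, but the sentence that follows presents 30 s as what the rule means, so either reading is open. The 10 s and 40 s shortfalls do depend on where the recording period starts; if it is a window before the reading, both shrink.

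Other safeguards count. Subjects agree to keep still and are told to stay motionless, and absent, blurred or question-marked values are dropped. These may leave very few affected pairs. They do not remove a normally displayed value that is still settling.

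The case report form itself is not in the documents, so movement times might be captured there; what can be said is that the listed steps do not ask for them. Finally, section 10.3 ties the primary objective to the RHEA confidence bounds alone, and section 10.4 sets no success criterion for the paired test. The possible harm is therefore confined to the secondary comparison and the equivalence argument drawn from it.

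**Conclusion.** The point holds. The stated rules conflict, and the conflict is lopsided: at a literal 30 s, the Reference Device is 30 s short of its own stable time and RHEA is not short at all. Any bias from that reading would favour RHEA in the section 10.4 comparison. It would not help RHEA in the primary test, where a RHEA reading kept at 20 to 30 s would, if anything, count against it.

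The size cannot be derived from the documents. Under the assumptions shown (one reading in 20 off by 5, in 10 to 25% of subjects) the mean reference RMSD rises by 0.01 to 0.06, which is small against half-widths of 0.11 to 0.25. It becomes material only if early readings are common or large, and may be near zero. Confidence is high that the text is inconsistent; no claim is made that a material bias will occur. It should be fixed because the direction favours the sponsor's device and, without movement times, the effect could not be checked afterwards.

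**What to change.** Reconcile sections 6.3, 10.2 and 10.4 so that recording and exclusion follow one rule per device, based on the plan's own stable times (30 s for RHEA, 1 min for the Reference Device):

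- Name the device in both 30 s sentences of 6.3.
- Replace the 20 s figure in 10.2 with the device-specific times, and have 10.4 refer to the Reference Device's own time.
- Define when the recording period starts.
- Add the time of any movement to the accuracy-test case report form.
- Report, next to the RMSD and separately for each device, how many readings were excluded for movement and how many for an absent, blurred or question-marked display.

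The cost is wording in three sections, one form entry and a short table. Tests would run slightly longer for restless subjects. The sample size of 73 (77 enrolled) does not change.

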10.3. Primary Analyses

For each subject, the RMSD will be calculated for both HR and RR. These individual values will be presented in both a listing and graphically as a cumulative distribution. The mean RMSD and its two-sided 95% confidence interval (mean RMSD \pm $t_{0.975} * \text{std err RMSD}$) will be presented. If the upper bound of the confidence interval is less than the hypothesized value, the corresponding null hypothesis will be rejected. For each rejected hypothesis, the study will have met its primary objective.

10.4. Secondary Analyses

Accuracy of the RHEA will be compared with that of the Reference Device-EarlySense device. The RMSD for the Reference Device will be calculated for each subject in the same manner as described for the RHEA. Mean accuracy will then be compared between the RHEA and the Reference Device by comparing the individual subject RMSDs by a paired t test at the 5% level of significance.

Bland Altman plots will be presented separately for each subject's raw data, including the limits of agreement, for both the RHEA and the Reference Device methods. In addition, Bland Altman plots will be presented for the set of RMSD estimates across all subjects, along with two-sided

95% confidence intervals for their limits of agreement. Finally, Bland Altman plots of the raw data across all subjects will be presented, along with two-sided 95% confidence intervals for their limits of agreement. Methods discussed in Bland, JM and Altman, DG (4) and (5) will be used to calculate the confidence intervals of the limits of agreement due to the lack of independence of the repeated measurements on the same subject.

Motion and no motion accuracy will each be calculated along with their respective two-sided 95% confidence intervals. Motion accuracy will be calculated as the proportion of times that the device correctly detected motion among all actual occurrences of motion detected manually. Non-motion accuracy will be calculated as the proportion of times that the device correctly did not detect motion among all actual occurrences of no motion detected manually.

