The RHEA Vital Sign Vigilance System was developed by Shenzhen Fiber Medical Technology Co. Ltd. It is designed for automatic, continuous and contact-less measurement of heart rate and respiratory rate of patients in a hospital or clinic setting. The system uses a sensor placed under the patient's mattress, and does not require a sensor to be fixed to the body. This provides a more comfortable solution for long-term continuous patient monitoring. Continuous monitoring of people's vital signs, in particular heart rate (HR) and respiratory rate (RR), may provide a mechanism to alert doctors or nurses of disease deterioration or an imminent severe clinical event. Monitoring people's vital signs outside an ICU often relies on nursing staff conducting checks at set intervals. The device can reduce the workload for nursing staff in non-ICU wards. The FDA-cleared EarlySense System 2.0 (K131379) developed by EarlySense Ltd. is also a contact-less system designed for continuous monitoring heart rate and respiratory rate of patients. It has been sold in over 20 U.S. hospitals since 2013. No recalls and adverse events have been reported. According to publicly available clinical results, the EarlySense System has shown an 86% reduction in Code Blue events, and a 45% reduction in Length of Stay (LoS) in the ICU for patients coming from the medical/surgical unit (1, 2). The EarlySense device applies the piezoelectric sensor while in comparison, the RHEA investigational device applies the optical fiber sensor. This difference leads to the RHEA device having a higher accuracy, capacity for greater patient weight range, longer sensor life and a lower cost. A Pilot Study on 25 healthy volunteers (20 adults and 5 children) showed that the RHEA device can obtain accuracy of overall mean root mean square difference (RMSD) of both HR and RR of 1.9 with the same testing procedure described in this current protocol (3). When comparing with the reference device- the EarlySense device on 9 adults, the RHEA device obtained results with no significant difference (pair t test is used to evaluate the results according to this protocol.)

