10.6. Sample Size

In a pilot study of 20 adult healthy volunteers with 20 paired observations each, the standard deviation of their RMSDs vs. the reference method were found to be approximately 0.75 for both HR and RR (2). Based on this standard deviation, 73 adult subjects will provide 80% power to reject each primary hypothesis if the population mean RMSD for HR is 3.0 and the population mean for RR is 2.0. To account for a dropout rate as high as 5%, a total of 77 adult subjects will be enrolled.

SAS Version 9.4 PROC POWER was used for all sample size calculations.

11. Regulatory and Reporting Requirements

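### Section 2.2 gives the statistical analysis the job of showing RHEA substantially equivalent to EarlySense, but 10.4 tests only for a difference, with no margin and no rule for equivalence

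*Combined protocol and SAP*

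**What the plan says.** Section 2.2 describes a statistical analysis that sets each contact-free device against the monitor, and says of that analysis: "to the MP/MX series separately aims to demonstrate that the investigational device is substantially equivalent to the cleared reference device-EarlySense System 2.0". Section 3 adds: "Comparison of the performance of the two contact-free devices will be performed on the recorded results via statistical analysis".

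Section 10.4 carries this out. A subject-level RMSD is computed for EarlySense in the same way as for RHEA, and mean accuracy is compared by "comparing the individual subject RMSDs by a paired t test at the 5% level of significance". The same section plans three sets of Bland-Altman plots: one per subject on raw data, one on the RMSD estimates across subjects, and a pooled one, described as "Bland Altman plots of the raw data across all subjects will be presented, along with two-sided 95% confidence intervals for their limits of agreement".

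The decision rule in Section 10.3 is of another kind. RHEA's mean RMSD is set against fixed values (3.25 for HR, 2.25 for RR): "If the upper bound of the confidence interval is less than the hypothesized value, the corresponding null hypothesis will be rejected". Section 10.6 sizes the trial for those tests only: "73 adult subjects will provide 80% power to reject each primary hypothesis".

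Section 2.1 reports an earlier comparison with EarlySense in 9 adults, in which "the RHEA device obtained results with no significant difference (pair t test is used to evaluate the results according to this protocol".

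**The concern.** The aim in 2.2 is a claim of similarity, and the test in 10.4 is built to detect a difference. Failing to find a difference may mean that the devices agree, or only that the comparison was imprecise; the p-value does not separate the two. In the other direction, a precise comparison can make a negligible disadvantage significant. With no margin and no stated rule, either outcome can be given a meaning after the data are seen.

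At stake is the comparative statement about EarlySense. The plan does not say what 73 subjects can show about it.

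**Working it through.** **1. The planned analyses against the aim.**
- 10.2 and 10.3: RHEA against the monitor, with fixed thresholds and a valid confidence-interval rule. EarlySense does not enter, and the thresholds are not tied to its accuracy.
- 10.4, paired t test: the only hypothesis test between the devices. The null is not written out; with no margin, it is a mean difference of zero.
- 10.4, Bland-Altman plots: the raw-data plots set each device against the monitor. The plot of RMSD estimates needs two values per subject, and the two RMSDs defined per subject for each vital sign are RHEA's and EarlySense's. It may therefore be a device-versus-device display with interval estimates. None of the plots has an acceptance limit.
- 10.5 and 10.6: no device-comparison criterion, margin or power.

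**2. The plan's own sample size.** One-sample t test, difference 0.25 (3.25 − 3.0 for HR, 2.25 − 2.0 for RR), SD 0.75, one-sided 0.025 (the two-sided 95% interval rule). The noncentral t calculation gives n = 73 with power 80.2%. Enrolment: 73/0.95 = 76.8, so 77. Both stated figures reproduce, for the primary tests only.

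**3. What the paired comparison could show (illustration).** Assumed:
- RMSD SD of 0.75 for both devices (10.6 gives it for RHEA, from 20 healthy adults)
- within-subject correlation ρ between the two RMSDs from 0 to 0.75
- a deficit or margin of 0.25, chosen because it equals the gap used in 10.6

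Formulas, with n = 73 and 72 degrees of freedom:
- SD of the paired difference = 0.75 × √(2(1 − ρ))
- 95% interval half-width = t(0.975, 72) × SD/√73, with t about 1.993
- noncentrality for 0.25 = 0.25 × √73/SD

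| ρ | SD of difference | 95% half-width | Noncentrality | Non-significant if RHEA truly 0.25 worse | Power for 'no worse', margin 0.25, true difference 0 |
|---|---|---|---|---|---|
| 0 | 1.061 | 0.247 | 2.01 | 49% | 51% |
| 0.25 | 0.919 | 0.214 | 2.33 | 37% | 63% |
| 0.5 | 0.750 | 0.175 | 2.85 | 20% | 80% |
| 0.75 | 0.530 | 0.124 | 4.03 | 2% | 98% |

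The last two columns sum to 100% because both use the same noncentrality. At ρ = 0.5 the SD of the difference is again 0.75, so the power matches the primary test's 80.2%.

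The half-width column also shows the opposite problem: an observed difference just above 0.247/0.214/0.175/0.124 would be significant, whether or not a difference of that size matters.

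**4. The 9-subject comparison in 2.1.** With n = 9 and the same assumptions, a true deficit of 0.25 would be non-significant 90/89/86/76% of the time at ρ = 0/0.25/0.5/0.75. Absence of significance there says little.

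**The case against.** Four arguments on the other side deserve weight.

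*The term may be regulatory.* Substantial equivalence covers safety and effectiveness and may be an overall device claim that needs no statistical margin. That is possible, since the protocol does not define it. But 2.2 names the statistical analysis as the means of demonstrating it, so either the analysis needs a rule or 2.2 needs rewording.

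*The test is secondary and the primary is sound.* This stands in full. The success criterion in 10.3 does not depend on the paired t test, which limits how serious the point is.

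*Some results would be informative.* This also stands. Section 2.1 claims higher accuracy for RHEA, and a significant result in that direction would support 'no less accurate'. A reader might infer that no result from 10.4 could support the comparative aim; that goes too far. The gap concerns a non-significant result or one favouring EarlySense.

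*The faulty inference is not planned.* A reader might infer that the sponsor will take non-significance as equivalence. The documents do not say so. The wording in 2.1 is background on a small pilot, although it does present non-significance by this same test as supporting evidence. The defect is that no rule is stated, not that a wrong one is.

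**Conclusion.** The point holds as a mismatch between 2.2 and 10.4: an equivalence aim is assigned to the statistics, and the device comparison has neither margin nor rule. This follows from the text and needs no assumption. It should be corrected before the data are seen.

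Its practical size is not known. The chance of missing a 0.25 deficit runs from 49% down to 2% depending on the correlation. The deficit, the EarlySense SD and the correlation are all assumed, so these figures only illustrate.

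A reader might also infer that 73 subjects are too few. The documents do not support this, because without a margin and a correlation there is nothing to judge 73 against. With an assumed margin of 0.25 and no true difference, power runs from 51% to 98%; with an assumed margin of 0.5 it is about 98% or higher at every correlation considered.

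**What to change.** In 10.4, for HR and RR separately:
- Report the mean paired difference in subject RMSD (RHEA minus Reference Device) with its two-sided 95% confidence interval.
- Conclude 'no less accurate' only if the upper limit is below a justified margin fixed before the data are seen. HR and RR may need different margins, as their primary thresholds differ.
- State that a non-significant difference is not evidence of equivalence.
- State whether both endpoints must pass.
- State whether the Bland-Altman plot of RMSD estimates compares the two devices.

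Reword 2.2 to match this conclusion, or drop the statistical equivalence claim from it.

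State the power at n = 73 for the chosen margin rather than enrol more. Under the assumptions above and no true difference, the smallest margin with 80% power per endpoint is about 0.353/0.305/0.249/0.176 at ρ = 0/0.25/0.5/0.75. If both endpoints must pass at margin 0.25, power is 26/40/64/96% when HR and RR are independent, rising to the per-endpoint figures when they are fully correlated.

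Cost: wording in 2.2 and 10.4 and one or two margins. The paired RMSDs are already planned, so no new data are collected. The downside is that the margins must be defended and the comparative conclusion becomes harder to reach.
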